6. DOSAGE AND TREATMENT ADMINISTRATION

6.1. Treatment Administration

For all subjects, KZR-261 will be administered as a 30- to 60-minute IV infusion via a central line on Days 1, 8, and 15 of a 4-week (28-day) treatment cycle. An IV infusion pump or syringe pump will be used for all infusions.

Further details regarding drug product formulation, preparation, and administration of KZR-261 will be provided in a separate Pharmacy Manual.

6.1.1. Monitoring of Dose Administration

Study treatment will be administered on an outpatient basis. Subjects should remain at the study site for observation for 6 hours following the first cycle, first dose (Cycle 1 Day 1) and for 2 hours following study treatment administration for the rest of Cycle 1 (Cycle 1 Days 8 and 15). For Cycle 2, subjects will be under observation for 1 hour following study treatment. For Cycle 3 and beyond, there is no required post-infusion monitoring.

This is a FIH study; therefore, treatment modifications for AEs may change as data are accrued. Subjects experiencing unacceptable AEs should have their treatment interrupted until resolution ([Section 6.1.2](#) and [Section 6.1.4](#)). Treatment with KZR-261 can then be reinitiated after consultation with the Medical Monitor.

6.1.2. Criteria for Interrupting Treatment During a Treatment Cycle

Within a treatment cycle, KZR-261 should be withheld on any scheduled treatment day if, during the previous 24 hours, the subject experiences any of the following events:

- \geq Grade 2 diarrhea, despite optimal anti-diarrheal therapy
- \geq Grade 2 vomiting, despite optimal anti-emetic therapy
- \geq Grade 3 fatigue that is not relieved by rest and limits self-care activities
- \geq Grade 3 transaminase elevation
- \geq Grade 2 amylase
- FBS \geq 200 mg/dL
- PLT count $<50 \times 10^9/L$
- ANC $<0.5 \times 10^9/L$
- Average QTcF >500 msec
- No resolution to \leq Grade 2 or baseline of previously reported Grade 3 or 4 events

6.1.3. Criteria for Initiation of a New Cycle

To commence treatment in Cycle 2 and beyond, subjects must meet the following criteria:

- ANC $\geq 1.25 \times 10^9/L$
- Hemoglobin $\geq 8 \text{ g/dL}$
- PLT count $\geq 75 \times 10^9/L$
- Serum creatinine $\leq 1.5 \times \text{ULN}$ (local institution) or calculated creatinine clearance $>60 \text{ mL/min}$ by the Cockcroft-Gault formula
- Total bilirubin $\leq 1.5 \times \text{ULN}$ (local institution)
- AST and ALT $\leq 3 \times \text{ULN}$ (local institution) or ALT and AST $\leq 5 \times \text{ULN}$ if the subject has hepatic metastases
- FBS $<200 \text{ mg/dL}$
- Serum amylase and lipase values $\leq 1.5 \times \text{ULN}$ (local institution)
- Average QTcF $<470 \text{ msec}$
- Resolution to \leq Grade 2 or baseline of any previously reported Grade 3 or 4 event

6.1.4. Dose Modification Guidelines for KZR-261

Dose reductions are not permitted during Cycle 1 (DLT assessment period) of Part 1 (Dose Escalation). If a subject experiences an event that qualifies as a DLT, as defined in [Section 3.2.3](#), the subject must be discontinued from study treatment and followed for resolution of AEs as described in [Section 9.1.5](#). Doses may be withheld or reduced for specific AEs and/or laboratory abnormalities in Cycles 2+ for subjects participating in Part 1 and in all cycles for subjects in Part 2 ([Section 6.1.4.2](#)).

Withheld doses should not be made up ([Section 6.1.5](#)).

6.1.4.1. Dose Interruptions

Subjects who experience an AE at any time during the study may interrupt study treatment per [Section 8.1](#). Subjects must continue to fulfill all criteria outlined in [Section 6.1.3](#) and not fulfill any of the criteria outlined in [Section 6.1.2](#) prior to each dose.

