Subjects who do not experience a DLT in Part 1, Cycle 1 (Dose Escalation) must receive all of their scheduled doses (Days 1, 8, and 15) with completed follow-up data available through 28 days of Cycle 1 to be eligible for DLT assessment. Subjects in Part 1, Cycle 1 who miss a dose for non-AE-related reasons will be replaced.

Both hematologic and non-hematologic DLTs include the following:

- Any AE that prevents the subject from receiving all planned doses during Cycle 1 (Doses may be held up to 7 days for resolution of non-DLT toxicity).
- Any AE that delays the initiation of Cycle 2 by >7 days because the AE has not resolved per criteria required for initiation of a new cycle ([Section 6.1.2](#) and [Section 6.1.4](#)).

Hematologic DLTs include the following:

- Grade 3 or 4 neutropenia (absolute neutrophil count [ANC] <1.0 × 10⁹/L) with a single temperature of >101°F (38.3°C), or microbiologically or radiographically documented infection.
- Grade 4 neutropenia (ANC <0.5 × 10⁹/L) in the absence of fever or infection lasting >7 consecutive days (complete blood count with differential must be measured every 2 to 3 days until recovery of ANC to ≤Grade 2).

- Grade 4 thrombocytopenia (platelet [PLT] count $<25 \times 10^9/L$) lasting >7 days (platelet counts must be measured every 2 to 3 days until recovery to \leq Grade 2 thrombocytopenia).
- Grade 3 or 4 thrombocytopenia (PLT count $<50 \times 10^9/L$) associated with clinically significant bleeding requiring platelet transfusion.

Non-hematologic DLTs include the following:

- Any non-hematologic AE \geq Grade 3, except the following:
 - Nausea, vomiting, diarrhea, electrolyte/metabolic abnormalities, constipation, fever, fatigue, or skin rash that resolves to \leq Grade 2 within 72 hours in the setting of optimal supportive care.
 - Grade 3 elevation in amylase or lipase without clinical or imaging manifestations of acute pancreatitis. In contrast, Grade 4 elevation in amylase or lipase and symptomatic Grade 3 lipase or amylase elevation are considered DLTs.
- Clinical signs and symptoms of acute pancreatitis.

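### The criteria for a within-cycle dose conflict, so it is unclear when a held Cycle 1 dose counts as missed and therefore as a DLT

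*Protocol*

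**What the plan says.** - **Protocol 6.1.2** covers dosing days inside a cycle: "Within a treatment cycle, KZR-261 should be withheld on any scheduled treatment day if, during the previous 24 hours" a listed event occurs. The list includes platelets <50, ANC <0.5, average QTcF >500 msec and transaminases at Grade 3 or above.
- **Protocol 6.1.3** covers the start of a cycle: "To commence treatment in Cycle 2 and beyond, subjects must meet the following criteria". These include platelets ≥75, ANC ≥1.25 and average QTcF <470 msec.
- **Protocol 6.1.4.1** joins the two for subjects with an AE at any time in the study: "Subjects must continue to fulfill all criteria outlined in" Section 6.1.3 "and not fulfill any of the criteria outlined in" Section 6.1.2 before each dose. **SAP 4.1.3.1** also applies both sections before each dose.
- **Protocol 6.1.4.2** lets a withheld drug resume within the same cycle by reference to 6.1.2, with platelets (no clinical bleeding) or ANC recovered to Grade 2. It describes 6.1.3 as the retreatment criteria for a new cycle.
- **Protocol 3.2.3** lists as a DLT "Any AE that prevents the subject from receiving all planned doses during Cycle 1", with a hold of up to 7 days allowed for toxicity that is not itself a DLT. Events attributed to the disease, intercurrent illness or concomitant medication are excluded.
- **Protocol 6.1.4** says that withheld doses are not given later.

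**The concern.** The missed-dose clause in 3.2.3 ties the DLT definition to the dosing rules. If a site cannot tell which criteria govern Days 8 and 15 of Cycle 1, it cannot tell in every case whether a dose should have been given.

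The specific DLT criteria show why this matters. The hematologic ones need Grade 4 cytopenia lasting more than 7 days, or Grade 3 or 4 with fever, infection or bleeding. Grade 3 amylase or lipase elevation without signs of pancreatitis is exempt from the general Grade 3 rule. If 6.1.3 applies to Day 8 or 15, a Grade 2 cytopenia, or a lipase above 1.5×ULN, bars the dose and could become a DLT through the missed-dose clause.

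DLTs are a primary endpoint of Part 1 and drive every i3+3 decision. A subject with a Cycle 1 DLT is also withdrawn from treatment and not replaced. About 8 sites are planned for Part 1, so different readings could be pooled in one DLT count.

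**Working it through.** No stated figure is in dispute, so the check compares the texts and then follows one subject through Table 1.

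**Step 1: compare the limits for a Day 8 or Day 15 dose** (counts ×10^9/L).

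| Item | 6.1.2 withholds if | 6.1.3 requires | Values where they differ |
|---|---|---|---|
| ANC | <0.5 | ≥1.25 | 0.5 to <1.25 |
| Platelets | <50 | ≥75 | 50 to <75 |
| Average QTcF (msec) | >500 | <470 | 470 to 500 |
| AST/ALT | Grade 3 or above | ≤3×ULN (≤5×ULN with hepatic metastases) | >3×ULN but below Grade 3, no hepatic metastases |
| Fasting blood sugar (mg/dL) | ≥200 | <200 | none |
| Hemoglobin, creatinine, bilirubin, lipase | no specific limit | limits given | only 6.1.3 sets a limit |

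The diarrhea, vomiting and fatigue holds are named only in 6.1.2. That section also withholds when an already reported Grade 3 or 4 event has not resolved to Grade 2 or baseline, so part of the ANC range below 1.0 may be held under both sections.

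**Step 2: find the direct contradiction.** Section 3.2.3 puts Grade 3 to 4 neutropenia at ANC <1.0 and Grade 3 to 4 thrombocytopenia at platelets <50. Recovery to Grade 2 is therefore reached at ANC 1.0 and platelets 50.

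- 6.1.4.2 allows resumption within the cycle from ANC 1.0 or platelets 50 (no clinical bleeding).
- 6.1.4.1, through 6.1.3, bars the dose until ANC is 1.25 or platelets are 75.
- Overlap: ANC 1.0 to <1.25 and platelets 50 to <75 are both allowed and barred.

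**Step 3: trace the route to a DLT.** All of these must hold in Part 1 Cycle 1:

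1. a value lies where the two sets differ on Day 8 or Day 15;
2. the site applies 6.1.3;
3. the event is not attributed to disease, intercurrent illness or concomitant medication;
4. the dose is still not given despite the hold of up to 7 days.

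Condition 4 is itself unclear. A Day 8 dose held the full 7 days reaches Day 8 + 7 = Day 15, the next dosing day, and 6.1.4 says withheld doses are not made up. The text does not say whether such a dose was delayed or missed.

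**Step 4: apply Table 1** (equivalence interval 0.25 to 0.35).

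- n=3: 0/3 = 0 is below the interval, escalate; 1/3 = 0.333 is inside, stay.
- n=6: 1/6 = 0.167 is below, escalate; 2/6 = 0.333 is inside, stay.

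These match Table 1. One reclassified subject changes the decision.

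**Step 5: sensitivity on an assumption.** The documents do not say how often Step 3 would occur. Suppose the DLT rate is 20% without it and it adds 0, 5, 10 or 20 points, giving rate p. With six subjects, Pr(escalate) = (1−p)^6 + 6p(1−p)^5:

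- p = 0.20: 0.262 + 0.393 = 0.655
- p = 0.25: 0.178 + 0.356 = 0.534
- p = 0.30: 0.118 + 0.303 = 0.420 (after rounding)
- p = 0.40: 0.047 + 0.187 = 0.233 (after rounding)

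This shows how sensitive the rule is to the assumed increment. It does not estimate the increment.

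**The case against.** **6.1.2 never orders a dose.** It lists reasons to withhold. 6.1.4.1 requires both tests, so it could mean simply that the stricter one applies. This stands for those two sections alone. A reader might infer that the plan says both treat and hold for every value in the Step 1 table; the text does not support that. The conflict comes from the stated scope of 6.1.3 and from the resumption rule in 6.1.4.2, and it is direct only for the ANC and platelet ranges in Step 2. The stricter reading also leaves the ANC, platelet and QTcF limits in 6.1.2 with no work to do.

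**6.1.3 may not reach Cycle 1.** Its scope starts at Cycle 2. Section 6.1.4 mentions withholding in Part 1 only for Cycles 2 and later, and the paragraph of 6.1.4.2 with the resumption rule opens with a sentence limited to outside the DLT period. This reading is available. Against it, 6.1.4.1 refers to any time in the study and each dose, SAP 4.1.3.1 agrees, and 3.2.3 itself allows holds in Cycle 1. No sentence settles the matter.

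**The 7-day hold absorbs many cases.** This stands. A reader might infer that any such value on Day 8 or 15 creates a DLT; Step 3 shows that it does not.

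**The SRC reviews each cohort before escalation.** True, and it can discuss individual cases, but the protocol gives it no rule on which criteria decide a missed dose.

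**Conclusion.** The inconsistency is real and lies in the current text of Protocol 6.1.3, 6.1.4.1 and 6.1.4.2 and of SAP 4.1.3.1. It bears on a primary endpoint because a single DLT can turn escalate into stay.

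The effect on the DLT count is conditional on all four parts of Step 3. A reader might go further and infer that the selected MTD would fall by some number of dose levels. The documents do not support that: they give neither the frequency of such values nor a dose-toxicity curve, and any added DLT rate would have to be assumed. The probabilities in Step 5 rest on that kind of assumption and on a 20% starting rate, so no MTD shift is claimed.

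The point should be corrected, but it does not invalidate the escalation design. No view is taken on which thresholds are right.

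**What to change.** The sponsor should reconcile Protocol 3.2.3, 6.1.2, 6.1.3, 6.1.4, 6.1.4.1 and 6.1.4.2 with SAP 4.1.3.1, so that:

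- one stated set of criteria governs doses within a cycle and one governs the start of a new cycle;
- the text says which set applies to Days 8 and 15 of Part 1 Cycle 1;
- the text says how that set, the hold of up to 7 days and the no-make-up rule together decide whether a Cycle 1 dose counts as missed for DLT purposes;
- cross-references agree. Section 3.2.3 cites 6.1.2 and 6.1.4, not 6.1.3, for starting a new cycle, and SAP 4.1.3.1 asks subjects to fulfill 6.1.2, which is a list of hold events.

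The choice of thresholds is for the sponsor. The cost is protocol wording and a matching SAP edit, with no change to sample size or to Table 1.

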6.1.4.2. Dose Modifications for Toxicity

Outside the DLT assessment period, dose modifications are to be discussed with the Medical Monitor prior to implementation to determine whether a dose modification is recommended. If KZR-261 is withheld for any toxicity within a treatment cycle, KZR-261 may be resumed **within that cycle** pending fulfillment of the criteria in [Section 6.1.2](#) to Grade 1 or baseline, platelet counts to Grade 2 without clinical bleeding, or absolute neutrophil counts to Grade 2 prior to the next scheduled treatment.

[Table 2](#) through [Table 7](#) summarize guidelines for KZR-261 treatment modifications for various potential toxicities encountered. The dose modifications detailed in these tables are based on toxicities encountered within a cycle to determine the most appropriate dose for initiation of a

subsequent treatment cycle (assuming that all the retreatment criteria for a new cycle as summarized in [Section 6.1.3](#) are met). Any dose reductions should be discussed with the Medical Monitor and documented in the source file and the eCRF.

Table 2: Dose Modifications for Isolated Transaminase Elevations

NCI-CTC AE Grade	Dose Adjustment
First episode of \geq Grade 3 ($>5\times$ baseline). Check transaminases at least twice per week until peak levels are reached, and then no less than weekly.	Withhold dose Resume dosing when elevations resolve to \leq Grade 2 and: 
• Reduce KZR-261 dose by one level if within a cycle• Subsequent cycles will begin at the reduced dose level
Second episode of \geq Grade 3 ($>5\times$ baseline). Check transaminases at least twice per week until peak levels are reached, and then no less than weekly.	Withhold dose Resume dosing at the subject's baseline grade and: 
• Reduce KZR-261 dose by one more level if within a cycle• Subsequent cycles will begin at the reduced dose level
Third episode of \geq Grade 3 ($>5\times$ baseline). Check transaminases at least twice per week until peak levels are reached, and then no less than weekly.	Discontinue KZR-261. Subject is not eligible to resume treatment.

Abbreviations: NCI CTCAE=Common Terminology Criteria for Adverse Events

Toxicity grades are per CTCAE v5.

Table 3: Dose Modifications for Thrombocytopenia

NCI CTCAE Grade	Dose Adjustment
Grade 3 thrombocytopenia with resolution to \leq Grade 2 within 1 week	No dose adjustment for subsequent cycles
Grade 3 thrombocytopenia without resolution to \leq Grade 2 within 1 week	Withhold dose until resolution to \leq Grade 2; no dose adjustment for subsequent cycles
Grade 4 thrombocytopenia or Grade 3 thrombocytopenia accompanied by clinically significant bleeding	Withhold dose until resolution of bleeding and/or thrombocytopenia to \leq Grade 2: 
• Dose reduce KZR-261 by one level if within a cycle• Subsequent cycles will begin at the reduced dose level

Abbreviations: NCI CTCAE=Common Terminology Criteria for Adverse Events

Table 4: Dose Modifications for Neutropenia

NCI CTCAE Grade	Dose Adjustment
≤Grade 3 neutropenia	No dose adjustment for subsequent cycles
Grade 4 neutropenia (duration <7 days) with resolution to ≤Grade 2 within 1 week	No dose adjustment for subsequent cycles
Grade 4 neutropenia (duration ≥7 days)	
 Withhold dose until ≤Grade 2 Reduce dose by one level if within a cycle, and begin subsequent cycles at the reduced dose level
Second episode of Grade 4 neutropenia (duration ≥7 days)	
 Withhold dose until ≤Grade 2 Reduce dose by one additional level if within a cycle, and begin subsequent cycles at the reduced dose level
Grade 3 or 4 neutropenia accompanied by fever (≥38.3°C)	
 Withhold dose until afebrile with resolution of neutropenia to ≤Grade 2 within 1 week; resume dosing without dose reduction. For a second episode of febrile neutropenia, reduce dose by one level if within a cycle, and begin subsequent cycles at the reduced dose level.

Abbreviations: NCI CTCAE=National Cancer Institute Common Terminology Criteria for Adverse Events

Table 5: Dose Modifications for Pancreatic Toxicity

NCI CTCAE Grade	Dose Adjustment
Amylase or lipase ≥Grade 3	Discontinue KZR-261
Hyperglycemia ≤Grade 1; amylase, lipase Grade 1 or Grade 2 without any symptoms.	No dose adjustment for subsequent cycles
Hyperglycemia ≥Grade 2 (ie, requiring treatment)	Withhold dose until ≤Grade 1, then: 
 Resume KZR-261 at the same dose or dose reduce one level if within a cycle Begin subsequent cycles at the same or reduced dose level

Abbreviations: NCI CTCAE=National Cancer Institute Common Terminology Criteria for Adverse Events

Table 6: Dose Modifications for Ocular Toxicity

NCI CTCAE Grade	Dose Adjustment
Cataract ≤Grade 2 or baseline; any other ocular toxicity ≤Grade 1 or baseline	No dose adjustment if within a cycle or for subsequent cycles unless slit-lamp examination reveals treatment-emergent progression of incidental, asymptomatic cataract that is considered at least possibly related to study drug. If progression occurred, reduce dose by one level.

Abbreviations: NCI CTCAE=National Cancer Institute Common Terminology Criteria for Adverse Events

Table 7: Dose Modifications for Other Toxicity

NCI CTCAE Grade	Dose Adjustment
≥Grade 3 with resolution to ≤Grade 2 or baseline within 1 week	Withhold dose until ≤Grade 1 or baseline, then: 
Resume KZR-261 at the same dose or reduce dose by one level if within a cycleBegin subsequent cycles at the same or reduced dose level
≥Grade 3 lasting ≥1 week	
Withhold dose until ≤Grade 1 or baselineReduce dose by one level if within a cycle, and begin subsequent cycles at a reduced dose level

Abbreviations: NCI CTCAE=National Cancer Institute Common Terminology Criteria for Adverse Events

Note:

- In the setting of Grade 2 toxicities not referenced above, including (but not limited to) nausea, vomiting, diarrhea, or fatigue that recur in successive cycles or are persistently debilitating in the opinion of the subject or Investigator, dose reduction by one level may be considered if within a cycle and for subsequent cycles and should be discussed with the Medical Monitor.

6.1.5. Missed Doses

Study treatment should be administered within the visit windows as per the Schedule of Events ([Appendix A](#) and [Appendix B](#)), with an exception for delays in dosing for up to 7 days duration for resolution of toxicity. Missed doses as a result of patient non-compliance will be considered protocol deviations.

Subjects who do not fulfill treatment interruption criteria ([Section 6.1.2](#)) or meet Individual Subject Stopping Rules ([Section 8.1.2](#)) may miss up to 2 consecutive doses or up to 6 doses in total over the first 6 cycles for any reason (eg, AE, scheduling, emergency). Subjects who require more than two dose reductions, or who miss one entire cycle because of an AE(s) must permanently discontinue KZR-261. Missed doses due to implementation of Study Stopping Rules ([Section 8.1.1](#)) should be discussed with the Medical Monitor to evaluate whether KZR-261 should be discontinued.

6.2. Prior and Concomitant Medications

A concomitant therapy is any therapy that may be administered (eg, transfusions, physical therapy, radiotherapy, surgery, medications). A concomitant medication is any prescription or over-the-counter preparation, including vitamins and supplements. All concomitant therapies must be recorded on the eCRF. Except as described below, prior medications used will be recorded for the 60 days prior to Screening until the first dose of study treatment. Concomitant medications will be recorded from first dose of study medication through 30 days after the last dose.

All prior anticancer treatments will be recorded on a separate, dedicated eCRF.

6.2.1. Permitted Concomitant Medications

6.2.1.1. Concurrent Supportive Care

Hematopoietic growth factors (eg, thrombopoietic agents such as romiplostim and eltrombopag, erythropoiesis stimulating agents, or granulocyte colony stimulating factors such as filgrastim and pegfilgrastim) are not permitted during Cycle 1 (the DLT assessment period, [Section 3.2.3](#)) for subjects in Part 1 (Dose Escalation) unless they are required for treatment of a DLT. In Cycles 2 and beyond, hematopoietic growth factors are permitted and may be used as clinically warranted and following institutional policies and recommendations. In case of severe or febrile neutropenia, growth factors may be used until neutrophil count recovery. In Part 2, hematopoietic growth factors may be used in Cycle 1 based on agreement between the Investigator and the Medical Monitor and in Cycles 2+ as per the aforementioned guidelines for Part 1.

Comprehensive supportive care is permitted during the study, including but not limited to anti-emetic and anti-diarrheal agents, appetite stimulants, stimulants with wakefulness-promoting properties (eg, modafinil), anticachexia therapy (eg, fish oil supplements), antidepressants, opiate and non-opiate analgesics, antibiotics, selective use of corticosteroids (≤ 20 mg daily prednisone or prednisone equivalent), therapies for diabetes mellitus, and platelet/neutrophil growth factors as indicated above. Anticoagulants except warfarin are also permitted.

Subjects with mCRPC are expected to continue on LHRH analogues if ongoing at Screening.

6.2.1.2. Other Concomitant Medications

Hormonal contraception is allowed. If using a hormonal form of contraception, use must have been stable for at least 4 weeks prior to Screening ([Section 4.2.1](#)). The same hormonal contraception should be continued for the duration of the study. If hormonal contraception is discontinued for safety reasons, the Investigator should ensure that the subject is using another acceptable form of contraception.

KZR-261 may affect medications that are substrates of CYP3A4. Administration of sensitive substrates of CYP3A4, or narrow therapeutic index drugs that are metabolized by CYP3A4 is not recommended from 14 days prior to the first dose of KZR-261 and during study treatment. If no alternative is available, please refer to the respective prescribing labels for dosing instructions. Medications that are sensitive substrates of CYP3A4, defined as those whose exposure may increase >5 -fold in the presence of CYP3A4 inhibition, are listed in [Appendix D](#).

